As all birth outcomes will have occurred as of the date of delivery, prevalence will be used as a measure of outcome occurrence.¹⁰ To allow for delayed reporting/diagnosis, all congenital malformations diagnosis recorded within one year of age will be included, according to the standard procedure used by the European Network of Congenital Anomaly Registers (EUROCAT)¹¹ through the end of 2016 in Denmark, Finland and Norway and through the end of 2017 in Sweden. In addition, available information on pregnancies ending in 2nd trimester therapeutic induced abortions will be identified in Denmark, Finland and Norway. Information on pregnancies ending in 2nd trimester therapeutic induced abortions is not available from Sweden for the specific study period. It will be especially important to identify pregnancy terminations due to malformations of the nervous system, as nearly half of the pregnancies affected by nervous system malformations may be terminated.¹²

Major congenital malformations and stillbirth prevalence will be described and compared using live and stillbirths as the denominator. For the birth outcomes other than major congenital malformations or stillbirth, prevalences at birth will be described and compared using live births as the denominator.

For the postnatal neurodevelopmental outcomes, livebirths of all gabapentin-exposed and the comparator pregnancies will be followed from the date of birth until the earliest record of a given outcome of interest, emigration (except Sweden and Norway, where emigration data are unavailable), death, or end of study (31 December 2016 in Denmark, Finland, and Norway; 31 December 2017 in Sweden); for this analysis, children in Norway born before 2008 will be excluded as the Patient Registry of Norway was launched in 2008. Thus, for the neurodevelopmental postnatal outcomes, livebirths will be followed up to a minimum of 1 year and a maximum of 8 years in Norway, 10 years postnatally in Denmark, and Finland, and up to a maximum 11.5 years postnatally in Sweden (Figure 2).

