9.3.2.2. Secondary Outcomes (Postnatal neurodevelopmental outcomes)

Postnatal neurodevelopmental outcomes (ICD-10 (International Classification of Diseases, Tenth Revision) codes):

- Attention-deficit hyperactivity disorders (F90);
- Pervasive developmental disorders (autism spectrum disorders) (F84);

- Learning disorders (Specific developmental disorders of speech and language (F80), and Specific developmental disorders of scholastic skills (F81)) and Intellectual disabilities (mental retardation) (F70-F79).

Follow-up for the postnatal neurodevelopmental outcomes, when available, will be a minimum of 1 year postnatally and for the maximum period available in the dataset for each birth. However, for a variety of reasons (e.g. emigration, death), follow-up could be infeasible in individual cases. It should be noted that not all livebirths will have available follow-up information into the school age, and as postnatal neurodevelopmental disorders are diagnosed primarily at school age, the number of events in gabapentin exposed (and other comparator groups) pregnancies in the study period may not be sufficient to yield stable estimates of association.¹⁶

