Table 4 shows the upper limit of the 95% confidence interval of risk ratio that can be ruled out with 80% probability, for different scenarios with respect to the size of the exposed and comparator groups based on counts provided in Table 3. The study size is estimated at greater than 3,000,000 pregnancies, including approximately 1743 exposed to gabapentin at any time. For example, a study of this size (1743 exposed to gabapentin at any time, 3,298,823 pregnancies in total) will rule out a relative risk with a 95% upper confidence limit of 1.5 with 80% probability, assuming the following: gabapentin vs. ‘unexposed to AEDs’ as comparator, background prevalence of major congenital malformations is 3%; gabapentin exposure prevalence is 0.8%; and the true underlying risk ratio is 1.0 (see Table 4).

Table 4. Upper limits of 95% confidence interval for risk or prevalence ratios depending on the prevalence of selected outcomes representative of prevalence of various study outcomes

Outcome	Estimated prevalence of outcome	Upper limit of 95% confidence interval for risk ratio can be ruled out with at least 80% probability (based on actual or estimated frequencies; approximate the analysis with gabapentin-unexposed as a comparator*)
Malformations of the nervous system ^{14,35} , mental retardation	0.2%	4.801 (use first-trimester counts)
Stillbirth, postnatal outcomes, ASD	0.6%	2.373 (use any time during pregnancy counts)
Cardiac congenital malformations, postnatal outcomes ^{12,14} , ADHD	1%	1.950 (use any time during pregnancy counts)
Any major congenital malformation ^{12,14}	3%	1.465 (use any time during pregnancy counts)
Preterm birth/SGA	10%	1.223 (use any time during pregnancy counts)
Upper limit of 95% confidence interval for risk ratio can be ruled out with at least 80% probability (based on actual or estimated frequencies; approximate the analysis with gabapentin-pregabalin as a comparator*)		
Malformations of the nervous system ^{14,35} , mental retardation	0.2%	7.069 (use first-trimester counts)
Stillbirth, postnatal outcomes, ASD	0.6%	2.977 (use any time during pregnancy counts)
Cardiac congenital malformations, postnatal outcomes ^{12,14} , ADHD	1%	2.324 (use any time during pregnancy counts)
Any major congenital malformation ^{12,14}	3%	1.619 (use any time during pregnancy counts)
Preterm birth/SGA	10%	1.289 (use any time during pregnancy counts)

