9.7.3. Estimation of prevalence ratios and hazard ratios

Crude and adjusted prevalence ratios and 95% Wald confidence intervals (CIs) for each birth outcome and a given population/contrast will be estimated using log-binomial regression.

Crude and adjusted incidence rate ratios and 95% Wald CIs will be estimated using Cox's proportional-hazards regression for each postnatal outcome. Crude and adjusted prevalence ratios and incidence rates ratios will be calculated for all pregnancies, including pregnancies with monotherapy exposure and pregnancies with polytherapy exposure, as well as the subset of only pregnancies with monotherapy exposure.

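### Table 4 sizes ADHD and ASD on births that the postnatal analysis excludes, so the printed limits are met with about 74-77% probability, not at least 80%, and the follow-up behind the assumed proportions is not stated

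*Protocol*

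**What the plan says.** Table 4 in section 9.5 is headed "Upper limit of 95% confidence interval for risk ratio can be ruled out with at least 80% probability". The accompanying text assumes "the true underlying risk ratio is 1.0" and gives the size as "1743 exposed to gabapentin at any time, 3,298,823 pregnancies in total". Against the unexposed, the ADHD row (1%) reads "1.950 (use any time during pregnancy counts"), the ASD row (0.6%) gives 2.373 on the same counts, and the mental retardation row (0.2%) reads "4.801 (use first-trimester counts"). These rows are shared with birth outcomes. The footnotes to Tables 3 and 4 say that no exclusion criteria were applied.

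The postnatal analysis is defined elsewhere:

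- Section 9.7.5 restricts it to live-born children and defines exposure as any time during pregnancy.
- Section 9.7.3 plans "proportional-hazards regression for each postnatal outcome".
- Section 9.2 states that "children in Norway born before 2008 will be excluded as the Patient Registry of Norway was launched in 2008".
- Section 9.2.1 ends the birth window on 31 December 2015 in Denmark, Finland and Norway. Table 3 is headed 2005-2016 for these countries.
- Follow-up ends on 31 December 2016 (2017 in Sweden). Section 9.3.2.2 warns that "not all livebirths will have available follow-up information into the school age" and that diagnosis comes mainly at that age.

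**The concern.** For an outcome fixed at birth, one proportion applied to every birth is a sound basis for precision. For a diagnosis made years later, precision depends on how many diagnoses occur in eligible children before follow-up ends. Table 4 treats both kinds of outcome alike. It counts children whom the postnatal analysis will not contain, and it does not say over what age or follow-up 1% of children are assumed to have an ADHD diagnosis or 0.6% an ASD diagnosis.

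Table 4 is the protocol's only quantitative statement of what the secondary neurodevelopmental objective can exclude. If its limits are too favourable, a null result for ADHD or ASD would look more reassuring than the design supports.

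**Working it through.** **1. Reproducing the printed limits.** At a true ratio of 1, SE = sqrt[(1-p)/p × (1/n1 + 1/n0)] and limit = exp[(1.960 + 0.842) × SE].

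- ADHD: p = 1%, n1 = 1,743, n0 = 3,298,823 - 1,743 = 3,297,080. SE = 0.2384, limit 1.950, with 17.4 expected exposed cases.
- ASD: p = 0.6%, same counts. SE = 0.3084, limit 2.373, with 10.5 expected exposed cases.
- Mental retardation: p = 0.2%, n1 = 1,592. SE = 0.5600, limit 4.801.

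All three match Table 4, so the calculation is a fixed proportion applied to all births.

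**2. Is the Cox model the reason?** The event-based form SE = sqrt(1/E1 + 1/E0), with the same expected events, gives 1.957 for ADHD and 2.379 for ASD. The choice of model makes almost no difference.

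**3. Eligible exposed births.** The any-time counts in Table 3 are 388 (Denmark), 388 (Finland), 467 (Norway) and 500 (Sweden). I assume births spread evenly over years. Table 3 scales in the same way: Norway's 657,451 births × 12/11 = 717,219.

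- Norwegian births of 2005-2007 removed only: 1,743 - 467 × 3/12 = 1,626, or 1,743 - 467 × 3/11 = 1,616 if the 467 cover 11 years.
- Births of 2016 also removed: 2 × 388 × 11/12 + 467 × 8/12 + 500 = 1,523, or 1,551 with 467 × 8/11.
- Stillbirths also removed at Table 4's 0.6%: 1,514 to 1,542.

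The unexposed group stays near 3 million and adds almost nothing to the SE.

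**4. Limits and probabilities, with 1% and 0.6% taken as the risks over each child's actual follow-up.** Probability of excluding a printed limit U = Φ[ln(U)/SE - 1.960].

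| Eligible exposed | ADHD limit | P(exclude 1.950) | ASD limit | P(exclude 2.373) |
|---|---|---|---|---|
| 1,626 | 2.00 | 77% | 2.45 | 77% |
| 1,616 | 2.00 | 77% | 2.45 | 77% |
| 1,551 | 2.03 | 75% | 2.50 | 75% |
| 1,523 | 2.04 | 74-75% | 2.52 | 74-75% |
| 1,514 | 2.05 | 74% | 2.53 | 74% |

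For example, with n1 = 1,514 and p = 1%: SE = 0.2558, limit = exp(2.802 × 0.2558) = 2.05, and ln(1.950)/0.2558 - 1.960 = 0.65, so the probability is 74%.

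**5. Conditional step: 1% as a risk reached by school age.** By the calendar dates, follow-up is spread evenly over 1-12 years in Denmark and Finland, 1-9 in Norway and 1-11.5 in Sweden. This is at least as generous as the maxima of 10, 8 and 11.5 years stated in section 9.2.

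- Linear accrual over ages 1-6. Average share of the risk observed: Denmark and Finland (5/11)/2 + 6/11 = 0.773; Norway (5/8)/2 + 3/8 = 0.688; Sweden (5/10.5)/2 + 5.5/10.5 = 0.762. The weighted share is about 0.75, which gives about 11.4 exposed cases, a limit of about 2.28, and about 62% probability of excluding 1.950.
- Linear accrual over ages 1-10. Shares 0.591, 0.444 and 0.571, weighted about 0.55. This gives about 8.4 exposed cases, a limit of about 2.61, and about 50% probability.

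**6. Mental retardation row.** Section 9.7.5 uses any-time exposure. With n1 = 1,743 the limit is 4.479 instead of 4.801, so the printed figure is conservative. Section 9.3.2.2 groups F70-F79 with F80 and F81, so no planned outcome is mental retardation alone.

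**The case against.** The strongest reply is that the simplification is disclosed. The footnotes state that no exclusions were applied, and the column heading calls the figures an approximation to the analysis. Sections 9.3.2.2 and 9.9 warn that postnatal events may be too few for stable estimates. Section 9.9 says that postnatal outcomes were made secondary because of measurement limits, and section 9.7.5 falls back on counts and crude rates if events are too few. The unconditional shortfall is also small. The removal of 2016 births is uncertain as well, because the Finnish and Norwegian gabapentin counts may already cover 2005-2015 only. In that case 388 × 11/12 + 388 + 467 × 8/11 + 500 = 1,583 are eligible, the limit is about 2.02 and the probability about 76%.

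These points limit the finding but do not remove it. A general warning does not make a printed probability true, and every count above gives less than 80%.

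A reader might infer more than the documents support:

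- **That the limits fail because the analysis is a Cox model.** Step 2 shows otherwise.
- **That the ADHD limit is really about 2.7, with 46% probability, or the ASD limit about 3.65.** Those figures apply the full risk to the roughly 770 exposed children who can be observed to age 6, and credit no diagnosis to anyone else. The protocol does not say that its proportions are risks by age 6, and a Cox analysis also counts earlier diagnoses.
- **That fewer than half of the children analysed reach age 6.** Among eligible births the share is about 50%, and age 6 is itself an assumption.
- **That the mental retardation row is also too favourable.** It errs in the other direction.

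**Conclusion.** Table 4's postnatal statement is wrong as written. The formula is applied correctly, but to the wrong population. With the protocol's own eligibility rules and exposed births spread evenly over years, about 1,514-1,626 exposed births remain. The limits become about 2.00-2.05 for ADHD and 2.45-2.53 for ASD, and 1.950 and 2.373 are excluded with about 74-77% probability. This holds on the most favourable reading of the assumed proportions.

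Any further loss from staggered follow-up depends on what 1% and 0.6% mean, which Table 4 does not say. If they are risks reached by school age, the ADHD figures fall to about 62% (accrual over ages 1-6) or about 50% (ages 1-10). That part is conditional and should be reported as such.

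**What to change.** Give the postnatal outcomes their own rows in Table 4, for the outcomes as analysed, including the combined learning disorder and intellectual disability outcome in place of mental retardation alone. For each row and all four comparators:

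- use any-trimester exposure and live births in the eligible years of each country;
- state the age or follow-up to which each assumed proportion applies;
- print the expected exposed and comparator events under the planned follow-up, with a range where the incidence is assumed;
- restate the limit from those events, or keep the present limit and print its lower probability.

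The cost is a recalculation and a revised table. No additional births are needed, but an age-specific incidence assumption must be stated, because the protocol does not give one. The limits for ADHD and ASD will be less favourable than those now printed.

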9.3.2.1. Primary Outcomes (Birth outcomes)

- Major congenital malformations, any and specific malformation type, according to the EUROCAT classification¹⁴
- Stillbirth, as recorded in each country's birth registry
- Low birth weight (birth weight < 2500 g)
- Small for gestational age (SGA), defined, for singleton pregnancies, as a dichotomous variable (yes/no) of birth weight below 2 standard deviations (SDs) of sex- and gestational week specific distributions, using country-specific reference standard.^{13,15} SGA non-singleton gestations will be defined if appropriate reference standard can be defined/identified; otherwise set to missing.
- Preterm birth, defined as gestational age <37 weeks
- Low Apgar score at 5 minutes, defined as a dichotomous variable (score 0-6 vs. score 7-10)
- Microcephaly, defined as a dichotomous variable (yes/no) of head circumference at birth (cm) smaller than 2 SD of sex- and gestational week specific distribution, using country-specific reference standard

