Upper limit of 95% confidence interval for risk ratio can be ruled out with at least 80% probability (based on actual or estimated frequencies; approximate the analysis with gabapentin-lamotrigine as a comparator*)		
Malformations of the nervous system ^{14,35} , mental retardation	0.2%	5.571 (use first-trimester counts)
Stillbirth, postnatal outcomes, ASD	0.6%	2.579 (use any time during pregnancy counts)
Cardiac congenital malformations, postnatal outcomes ^{12,14} , ADHD	1%	2.080 (use any time during pregnancy counts)
Any major congenital malformation ^{12,14}	3%	1.520 (use any time during pregnancy counts)
Preterm birth/SGA	10%	1.247 (use any time during pregnancy counts)
Upper limit of 95% confidence interval for risk ratio can be ruled out with at least 80% probability (based on actual or estimated frequencies; approximate the analysis with gabapentin-pregabalin or lamotrigine as a comparator*)		
Malformations of the nervous system ^{14,35} , mental retardation	0.2%	5.447 (use first-trimester counts)
Stillbirth, postnatal outcomes, ASD	0.6%	2.547 (use any time counts)
Cardiac congenital malformations, postnatal outcomes ^{12,14} , ADHD	1%	2.060 (use any time counts)
Any major congenital malformation ^{12,14}	3%	1.511 (use any time counts)

Table 4. Upper limits of 95% confidence interval for risk or prevalence ratios depending on the prevalence of selected outcomes representative of prevalence of various study outcomes

Preterm birth/SGA	10%	1.243 (use any time counts)
-------------------	-----	-----------------------------

*Can include exposed to other AEDs i.e., monotherapy or polytherapy; calculations made without applying any exclusion criteria. The computations were done using SAS software based on the ‘Study size’ worksheet of the Episheet.⁴⁸

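### Table 4 plans SGA at 10% prevalence, which does not fit the protocol's below-2-SD definition, so the stated limits for SGA are too favourable

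*Protocol*

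**What the plan says.** Section 9.5 presents Table 4 as the "upper limit of the 95% confidence interval of risk ratio that can be ruled out with 80% probability", given that "the true underlying risk ratio is 1.0". The counts for exposure at any time are "1743 exposed to gabapentin at any time, 3,298,823 pregnancies in total". Each of the four comparator blocks has a row labelled "Preterm birth/SGA" with an estimated prevalence of 10%. The entries are "1.223 (use any time during pregnancy counts") against unexposed, 1.289 against pregabalin, "1.247 (use any time during pregnancy counts") against lamotrigine, and 1.243 against pregabalin or lamotrigine. The row gives no source for the 10%.

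Section 9.3.2.1 lists SGA as a primary outcome and defines it, for singletons, "as a dichotomous variable (yes/no) of birth weight below 2 standard deviations (SDs) of sex- and gestational week specific distributions", using a country-specific reference. Microcephaly follows the same rule: "head circumference at birth (cm) smaller than 2 SD of sex- and gestational week specific distribution". Sections 9.2 and 9.7.1 use live births as the denominator for both.

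**The concern.** The planning prevalence and the outcome definition do not describe the same variable. On a normal reference, a 10% prevalence corresponds to a cut-off at about -1.28 SD, the 10th percentile. The protocol does not use that cut-off. A cut-off at -2 SD selects far fewer births, so there are far fewer SGA events and the interval is wider.

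SGA is a primary outcome of a study done as a commitment to the EMA, and Table 4 is the protocol's statement of what the study can exclude. As written, it says that an SGA increase of about 22% over unexposed births can be ruled out with 80% probability. Someone planning to interpret a null SGA result from this table would expect more than the data can give.

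**Working it through.** **Inputs**

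- Two-sided 95% interval (z = 1.960), 80% probability (z = 0.842), true ratio 1.0: section 9.5. Sum of z values: 2.8016.
- Exposed at any time, n1 = 1,743. Total 3,298,823, so n0 = 3,298,823 - 1,743 = 3,297,080 for unexposed.
- n0 = 2,930 for pregabalin and 8,584 for lamotrigine at any time: Table 3.
- Pregabalin or lamotrigine: Table 3 gives no combined count (see below).
- SGA prevalence: not given in the protocol for a 2 SD rule. Assumption: a normal reference that fits the population, so p = Φ(-2) = 0.02275, with a range of 2-4%.

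**Formula**

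U = exp{2.8016 × sqrt[((1 - p)/p) × (1/n1 + 1/n0)]}

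**Reproducing the protocol at p = 0.10, against unexposed**

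- Standard error = sqrt[9 × (1/1,743 + 1/3,297,080)] = 0.0719.
- U = exp(2.8016 × 0.0719) = 1.223, as stated.

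The same formula returns the other any-time limits against unexposed (2.373, 1.950, 1.465) and the 10% entries against pregabalin (1.289) and lamotrigine (1.247). The method is therefore established and the arithmetic is correct for 10%.

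**Count for the fourth comparator**

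Adding the Table 3 counts gives 2,930 + 8,584 = 11,514. This does not reproduce the stated limits: it gives 2.526, 2.047, 1.506 and 1.241 where Table 4 has 2.547, 2.060, 1.511 and 1.243. A count of about 10,150 fits all four, so 10,150 is used here. The sum would also count pregnancies dispensed both drugs twice.

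**SGA at a prevalence that fits 2 SD, against unexposed**

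- (1 - p)/p = 0.97725/0.02275 = 42.96.
- Standard error = sqrt[42.96 × (1/1,743 + 1/3,297,080)] = 0.1570.
- U = exp(2.8016 × 0.1570) = 1.553.

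| Comparator | Stated (10%) | p = 2% | p = 2.275% | p = 4% |
|---|---|---|---|---|
| Unexposed | 1.223 | 1.600 | 1.553 | 1.389 |
| Pregabalin | 1.289 | 1.810 | 1.743 | 1.515 |
| Lamotrigine | 1.247 | 1.674 | 1.620 | 1.434 |
| Pregabalin or lamotrigine (n0 about 10,150) | 1.243 | 1.663 | 1.610 | 1.427 |

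**Chance of excluding 1.223 against unexposed**

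Φ[ln(1.223)/SE - 1.960] = Φ(0.2013/0.1570 - 1.960) = Φ(-0.68) = 0.25. At 2% it is 0.22, at 3% 0.31 and at 4% 0.40. At 10% the formula returns the intended 0.80.

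**Expected exposed SGA cases**

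1,743 × 0.10 = 174, against 1,743 × 0.02275 = about 40 (35 at 2%, 70 at 4%).

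**Restriction to singleton live births**

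The counts above include multiples and stillbirths, which the SGA analysis largely drops. If 3-5% of births were lost (an assumption), the limit against unexposed at 2.275% would be 1.563-1.570.

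**The case against.** The strongest reply is that 2.3% appears nowhere in the protocol. It needs a normal reference that is calibrated to these births, and the country references cannot be seen from the document. That stands, so the supportable statement is a range (1.39 to 1.60 against unexposed), not a single replacement value. It does not rescue 10%. Even at 5% the limit would be 1.34, and the only other 10% for SGA in the protocol is the unexposed figure of a cited Italian study in section 7, whose cut-off is not stated.

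A second reply is that nothing in the conduct of the study depends on this row. All registry births in a fixed period are included, the worked example in section 9.5 concerns malformations at 3%, and estimates will carry 95% intervals that show the real SGA precision. This also stands. It limits the consequence to the planning statement, and that statement remains wrong for SGA.

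A third reply is that the Table 4 caption calls the outcomes selected and representative. That covers outcomes without a row, but not one that is named and given a prevalence at odds with its definition.

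A reader might also infer that Table 4 contains a calculation error, or that the absence of a microcephaly row is a fault. Neither is supported. The stated limits reproduce at 10%. A table of selected outcomes need not list microcephaly; low birth weight and low Apgar score have no row either.

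**Conclusion.** The point holds as an inconsistency between a planning prevalence and an outcome definition. For SGA as defined, the limits that can be ruled out with 80% probability are about 1.55 against unexposed, 1.74 against pregabalin, 1.62 against lamotrigine and 1.61 against either drug. On the log scale the excess that can be ruled out against unexposed roughly doubles, from ln 1.223 = 0.20 to ln 1.553 = 0.44.

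The central values assume a normal, well-calibrated reference, the any-time counts of Table 3 without exclusions and, for the fourth comparator, a count inferred from the protocol's own limits. The direction does not depend on those details: throughout 2-4% every limit is well above the stated one, and restriction to singleton live births moves the limits slightly further up.

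It would be too strong to say that the limit is exactly 1.55, or that the SGA analysis is invalid. The definition and the analysis are unaffected, and the preterm birth part of the row is not in question here.

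**What to change.** Keep the 2 SD definition of SGA. In each of the four blocks of Table 4, split the shared row: leave preterm birth in its own row, and give SGA a separate row at a prevalence consistent with the definition. That prevalence should either be about 2.3%, stated as an assumption with a range, or be taken from the country references chosen for the analysis. Restate the four limits from it, preferably on singleton live births and with the actual count for pregabalin or lamotrigine. Microcephaly could share the row, since it uses the same rule, but that is optional.

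The cost is one table row per comparator block and a less favourable stated precision for SGA. Data, definitions and analyses do not change.
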